Patients will receive Cetuximab intravenous infusions at a dose of 500 mg/m² to be administered over 2 hours and thereafter fortnightly infusions. Cetuximab is provided in ready use vials containing 5 mg/ml. Once removed from the vial, Cetuximab must be used within 8 hours if stored at room temperature.

Please note Cetuximab must be administered under the supervision of a physician experienced in the use of antineoplastic medicinal products. Close monitoring is required during the infusion and for at least 1 hour after the end of the infusion. Availability of resuscitation equipment must be ensured. Vital signs should be checked and recorded before, during, and 1 hour after the Cetuximab infusion. There must be at least one hour between completion of Cetuximab and the start of chemotherapy.

Day 1 of treatment schedule (14 day cycle)

0:00	IV Chlorphenamine 10mg, Paracetamol 1g p.o., ranitidine 150mg p.o. IV bolus Dexamethasone 8 mg IV bolus Granisetron 3 mg (or equivalent) Flush line with 0.9% saline
0:00-2:00	Cetuximab 500 mg/m ² IV infusion, 2 hours Flush line with 0.9% saline
2:00-3:00	Observe for delayed hypersensitivity reaction Flush line with 5% Dextrose
3:00-3:30	Irinotecan 180 mg/m ² IV infusion over 30 minutes in 250 ml normal saline
3:30-5:30	l -folinic acid (175 mg flat dose) or d,l -folinic acid (350 mg flat dose) IV infusion, 2 hrs, 250 ml 5% Dextrose Flush line with 5% Dextrose
5:30-5:35	5-Fluorouracil 400 mg/m ² IV bolus over 5 minutes
5:35-51:30	5-Fluorouracil 2400 mg/m ² IV infusion over 46 hours
51:30	Disconnect pump and flush line (5 ml heparinised saline)
Day 4-14	No treatment

Notes:

- The 1st dose of Cetuximab (500 mg/m²) should be administered by i.v. infusion **over 120 minutes**. There must be at least one hour between completion of Cetuximab and the start of chemotherapy.
- The 2nd dose of Cetuximab (500 mg/m²) should be administered by i.v. infusion **over 90 minutes**. There must be at least one hour between completion of Cetuximab and the start of chemotherapy.

- **Subsequent doses** of Cetuximab (500 mg/m²) should be administered by i.v. infusion **over 60 minutes**. There must be at least one hour between completion of Cetuximab and the start of chemotherapy.
- Observations continue as on day 1 and the one hour gap between Cetuximab and chemotherapy should be maintained.
- Bolus 5FU is recommended to be given over 5 minutes but may be administered as a 15 or 30 minute infusion where this reflects local practice.
- Do not use injection equipment containing aluminium.
- The use of pre-packed 'minibags' of 5FU is acceptable.
- Please check with the UoSCTU if your local policy for pre-chemotherapy medication differs to that stated here to confirm if it is acceptable for use in the trial.

Oral antiemetics (starting day 2):

- Dexamethasone 4 mg tds x1 day; 4 mg bd x1 day; 4 mg od x1 day.
- Domperidone or metoclopramide prn.
- Ensure patient has supplies of Loperamide and Ciprofloxacin, and knows how to use them.

Note on the use of dexamethasone

- For patients at high risk of steroid side effects (e.g. diabetics) or for those who develop toxicity attributable to steroids (e.g. dyspepsia; dysphoria; etc), the oral steroid should be omitted.

Scheduled tests

- FBC and clinical assessment (NCI toxicity scores) should be performed on the day of starting each cycle (or within 3 working days before) and the results available before starting.
- Biochemistry (including creatinine, bilirubin, magnesium and either AST or ALT) is done at the same time as FBC.
- If patient is clinically jaundiced bilirubin level must be reviewed prior to administration of Oxaliplatin.
- If patient has symptoms of possible hypomagnesemia, check magnesium level and correct as advised (see Appendix XIII).

Toxicity and dose adjustments for IrMdG plus Cetuximab

Allergic/hypersensitivity reactions - Cetuximab

- Severe grade 3/4 hypersensitivity reactions have occurred in 2.2% of patients treated with Cetuximab. One death from angio-oedema has been reported.

- Signs include rapid onset of airway obstruction, urticaria and/or hypotension. 80% occur during or within one hour of the first infusion, but reactions can occur with later infusions.
- **Cetuximab must be administered under the supervision of a physician experienced in the use of antineoplastic medicinal products. Close monitoring is required during the infusion and for at least 1 hour after the end of the infusion. Availability of resuscitation equipment must be ensured.**
- Treatment depends on the grade or severity of the reaction, as follows:

CTC Grade Allergic/hypersensitivity reaction	Treatment
Grade 1 Transient flushing or rash, drug fever <38°C	Decrease the Cetuximab infusion rate by 50% and monitor closely for any worsening. The total infusion time for Cetuximab should not exceed 240 minutes (4 hours).
Grade 2 Rash; flushing; urticaria; dyspnea; drug fever ≥ 38°C	Stop Cetuximab infusion. Administer bronchodilators, oxygen etc. as medically indicated. Resume infusion at 50% of previous rate once allergic/hypersensitivity reaction has resolved or decreased to grade 1 in severity, and monitor closely for any worsening.
Grade 3 or Grade 4 Grade 3: Symptomatic bronchospasm, with or without urticaria; parenteral medication(s) indicated; allergy-related oedema/angioedema; hypotension Grade 4: Anaphylaxis	Stop Cetuximab infusion immediately and disconnect infusion tubing from the patient. Administer adrenaline, bronchodilators, antihistamines, glucocorticoids, intravenous fluids, vasopressor agents, oxygen etc., as medically indicated. Patients have to be withdrawn immediately from treatment and must not receive any further Cetuximab treatment.

- Once the infusion rate has been slowed for an allergic reaction, it should remain at the slower rate for all subsequent infusions.
- If the patient has a second allergic/hypersensitivity reaction on the slower infusion rate, the infusion should be stopped and no further Cetuximab administered.

- If a patient receives a grade 3 or 4 allergic/hypersensitivity reaction at any time, Cetuximab must be discontinued.
- If there is any doubt whether a reaction is an allergic/hypersensitivity reaction of Grades 1-4, the trial principal co-investigator [name] should be contacted immediately to discuss and grade the reaction.

Skin toxicity - Cetuximab

[figure not shown]
- The acneiform skin rash associated with Cetuximab occurs in over 70% of patients. About 12% have grade ≥ 3 reactions. On longer-term therapy, paronychia occurs in about 10% of patients and can be painful.
- Discussion with a local dermatologist prior to study initiation would be helpful to agree local plans of management and mechanisms for rapid referral in case of severe skin toxicity.
- The occurrence of the rash has been correlated with an increased likelihood of response to treatment, though this information needs to be used with caution, as it is not a direct correlation.
- The rash usually occurs on the face, upper chest and back with multiple follicles and pustules. The onset is usually within the first 3 weeks of treatment and many cases improve by 12 weeks on treatment.
- Dose modifications for grade 3 toxicity are summarised on the algorithm below. For CTC grade 1 or 2: continue treatment with Cetuximab. If a patient experiences grade 3 skin toxicity (rash effects $> 50\%$ of body surface area), Cetuximab therapy may be delayed for up to 14 days without changing the dose level. If grade 3 skin toxicity occurs for a second and third time, Cetuximab therapy may again be delayed for up to 14 days with concomitant dose reductions to 400 mg/m^2 and then 300 mg/m^2 . Cetuximab dose reductions are permanent. Patients must discontinue Cetuximab if more than 2 consecutive infusions are withheld or grade 3 skin toxicity occurs for a fourth time despite appropriate dose reduction. If the toxicity resolves to grade 2 or less by the following treatment period, treatment may be resumed.
- The investigator should also consider concomitant treatment with topical and oral antibiotics. Grade 1 acneiform eruption: consider treatment with topical antibiotics (e.g. topical metronidazole or erythromycin). Systemic antibiotics (e.g. a second generation tetracycline such as doxycycline 100mg po daily) should be considered for grade 2 acneiform eruption, and are mandatory for grade ≥ 3 reactions. The threshold for referral to the dermatology clinic should be planned locally but all patients with grade ≥ 3 reactions and probably all with grade 2 reactions should be referred for advice and management. If pruritus occurs an oral antihistamine is advised. Dry skin often occurs (and may contribute to pruritus) general advice on replacing soap with oil for washing, avoidance of hot water for baths or showers and use of emollient creams are beneficial; topical corticosteroids can be used according to local practice. Fissures may occur in dry skin and topical dressings (e.g. hydrocolloid dressings and as advised by your dermatologist) are helpful.

- Colloidal oatmeal preparations (Aveeno, Nature's Gate) can be effective if applied at least 3 times daily⁴⁸. These are available at chemists or on the internet.
- Nail toxicities occur in 8% of patients with Cetuximab, characterised by a paronychia inflammation with associated swelling of the lateral skin folds of toes and fingers, especially great toes and thumbs, which may be painful. It may persist for up to three months after cessation of Cetuximab therapy. Dermatological advice should be sought. Use of daily salt baths and local antiseptic / astringent ointments have been found to be helpful. Anti-inflammatory drugs may help to ease the pain.

Hypomagnesaemia - Cetuximab

- Hypomagnesaemia has been reported in up to 65% of patients following Cetuximab therapy. Patients should have magnesium concentration monitored at baseline, prior to each cycle of chemotherapy and for up to 8 weeks after the last dose of chemotherapy, or until magnesium has normalised, whichever is the longer.
- Fatigue, malaise, tremor, ataxia, carpopedal spasm, hyperreflexia, confusion, hallucinations, convulsions and arrhythmias may occur.
- Hypomagnesemia should be corrected by intravenous supplementation if grade 3 (<0.4 mmol/l) or symptomatic. If lesser degrees of hypomagnesemia are detected, oral supplementation may be considered (see Appendix XIII for details).
- Dose modifications for grade 3 toxicity are summarised in the algorithm below. For CTC grade 1 or 2: continue treatment with Cetuximab. If a patient experiences grade 3 toxicity, Cetuximab therapy may be delayed for up to 14 days without changing the dose level. If grade 3 toxicity occurs for a second and third time, Cetuximab therapy may again be delayed for up to 14 days with concomitant dose reductions to 400 mg/m² and then 300 mg/m². Cetuximab dose reductions are permanent. Patients must discontinue Cetuximab if more than 2 consecutive infusions are withheld or grade 3 toxicity occurs for a fourth time despite appropriate dose reduction. If the toxicity resolves to grade 2 or less by the following treatment period, treatment may be resumed.

Dose modifications for Cetuximab-related skin toxicity and hypomagnesaemia:

* These refer to the second and third consecutive week of non-resolving grade 3 toxicity.

Acute cholinergic syndrome

- Irinotecan may provoke an acute cholinergic syndrome with diarrhoea, sweating, salivation, bradycardia, etc. This may start during the drug infusion or shortly after.
- If this occurs, give atropine sulphate 0.25 mg s/c immediately. Atropine should then be given prophylactically with subsequent cycles.

Haematological

- Myelotoxicity is commoner with IrMdG than with MdG. Leucopenia has been reported and attributed to Cetuximab in 8% of patients treated with chemotherapy plus Cetuximab.
- Check FBC on (or up to 3 working days before) day 1 of each cycle. Delay 1 week if WBC $< 3.0 \times 10^9/l$, granulocytes $< 1.5 \times 10^9/l$ or platelets $< 100 \times 10^9/l$. Only treat when WBC and platelets are above these limits.
- If >1 delay, or 1 delay of ≥ 2 weeks occurs, reduce the Irinotecan and 5FU (bolus and infusion) doses by 20% and continue at the lower dose for subsequent cycles unless further toxicity occurs.
- If a further delay(s) for myelotoxicity occurs despite a 20% dose reduction, a further dose reduction may be made, at the discretion of the treating clinician.

Neurotoxicity

- Neurotoxicity (cerebellar) is uncommon; consider changing to alternative treatment.
- Changes in treatment should be discussed with one of the clinical coordinators.

Renal function (see also Appendix IV)

- Check serum creatinine at each cycle. If this rises $>25\%$, re-check EDTA clearance or 24-hour urinary clearance, and adjust Irinotecan and 5FU doses according to the table in Appendix IV.
- Patients with moderate renal impairment may receive irinotecan, but if GFR $<30ml/min$, the Irinotecan dose should be reduced by 50% and the 5FU dose should be reduced by 25% (see Appendix IV).
- There is little experience of administering Cetuximab in patients with renal insufficiency. Physicians should exercise caution and consider a dose reduction. No specific guidelines are available.

Hepatobiliary function (see also Appendix IV)

- Irinotecan and its metabolites are cleared by biliary excretion and patients with cholestasis have delayed clearance.
- LFTs should be checked before each treatment cycle. Patients with serum ALP $>5 \times ULN$ or serum bilirubin in the range $1.5-3 \times ULN$ require a 50% dose reduction of irinotecan; patients with serum bilirubin $>3 \times ULN$ should not receive Irinotecan (please refer to Appendix IV).

- 5FU should be reduced by 50% in patients with serum bilirubin $>3 \times$ ULN (see Appendix IV).
- Transaminase (either AST or ALT) $\leq 2.5 \times$ ULN is required for study entry. An isolated rise in transaminase above $2.5 \times$ ULN during treatment is likely to be treatment-related, and treatment should be interrupted until recovery (see Appendix IV).
- Bilirubin $\leq 1.25 \times$ ULN is required for study entry. If bilirubin rises above this limit during treatment, discuss with treating investigator as this may indicate disease progression. If treatment is to continue, please refer to table in Appendix IV.
- There is little experience of administering Cetuximab in patients with hepatic insufficiency. Physicians should exercise caution and consider a dose reduction. No specific guidelines are available.

Interstitial pneumonitis

- A syndrome of severe acute interstitial pneumonitis has been reported recently with another EGFR targeted therapy, gefitinib.
- Should a patient develop severe dyspnoea and/or hypoxia, seek urgent assistance from a chest physician. A high resolution CT scan of thorax, bronchoscopy plus transbronchial biopsies for pathology and relevant cultures should be considered.
- Cetuximab should be withheld until complete resolution of the toxicity.

Stomatitis

- Routine mouthcare (e.g. Corsadyl, nystatin) is recommended, local policy on the use of these or similar drugs is acceptable.
- If mouth ulcers occur despite this, reduce the 5FU doses (bolus and infusion) by 20% and continue at the lower dose for subsequent cycles unless further toxicity occurs.
- If further toxicity occurs reduce 5FU doses (bolus and infusion) by a further 20%.
- Stomatitis occurs in about 10% of patients treated with Cetuximab. It has not been considered an indication for dose reduction in previous trials. However, if stomatitis continues despite 5FU dose reduction, Cetuximab dose reduction to $400\text{mg}/\text{m}^2$ should be considered.

Diarrhoea

- Irinotecan may produce delayed diarrhoea which, if untreated, may become severe. Early intervention with high-dose Loperamide is highly effective. Patients must be carefully instructed and given the written information sheet, telephone contact numbers and supplies of Loperamide and Ciprofloxacin. Care should be taken that out-of-hours staff answering patient queries are familiar with the protocol.
- Patients should start Loperamide at the first loose stool: 4 mg, then 2 mg every 2 hours until 12 hours after the last loose stool (up to a maximum of 48 hours).
- If diarrhoea lasts > 24 hours, Ciprofloxacin 500 mg bd should be added. If it lasts > 48 hours, or if the patient reports symptoms of dehydration, admit acutely for rehydration and further management (eg octreotide).
- After an episode of severe diarrhoea (grade 3-4), delay chemotherapy until full recovery then resume at 20% reduced doses of Irinotecan and 5FU (bolus and infusion).

- If diarrhoea from the previous cycle, even if not severe, has not resolved by the time the next cycle is due, delay 1 week.
- If diarrhoea persists, Cetuximab dose reduction to 400mg/m² should be considered.

Hand-foot syndrome (HFS)

- Treat symptomatically. Pyridoxine 50 mg tds by mouth or topical corticosteroids may help.
- If HFS is still a problem, reduce the 5FU doses (bolus and infusion) by 20% for subsequent cycles (no need to reduce irinotecan).
- If further toxicity occurs reduce 5FU doses (bolus and infusion) by a further 20%.

DPD deficiency; cardiotoxicity

- DPD is the initial and rate-limiting enzyme for 5-FU breakdown. DPD deficiency is an inherited (pharmacogenetic) disorder in which individuals with absent or significantly decreased DPD activity develop life-threatening toxicity following exposure to 5-FU (in either IV or oral form). Reduced drug clearance results in markedly prolonged exposure to 5-FU so that administration of standard doses of 5-FU results in altered 5-FU pharmacokinetics and severe toxicity including mucositis, granulocytopenia, neuropathy and death. The onset of toxicity usually occurs twice as fast in patients with low DPD activity as compared with patients with a normal DPD activity. Approximately 3-5% of the population has low DPD activity and 0.1% have absent activity. We recommend that (i) patients with a personal or family history suggestive of DPD deficiency should not be enrolled onto New EPOC, and (ii) those who experience grade 3/4 neutropenia and grade 3/4 mucositis after cycle 1 should be considered as potentially having DPD deficiency. If DPD deficiency is suspected, patients should only continue on trial after full recovery but without the further use of a Fluoropyrimidine.
- 5FU may provoke angina attacks or even MI in patients with ischaemic heart disease. Continued treatment with upgraded antianginal medication and reduced 5FU dose may be considered.

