- Patients requiring ongoing treatment with a contraindicated concomitant medication.
- Patients with another previous or current malignant disease which, in the judgement of the treating investigator, is likely to interfere with New EPOC treatment or assessment of response.
- Patients with known hypersensitivity reactions to any of the components of the study treatments.
- Patients with distant metastases outside the liver.
- Female patients who are lactating.
- Patients with a personal or family history suggestive of dihydropyrimidine dehydrogenase (DPD) deficiency or with known DPD deficiency.
- Patients who possess the kRAS-mt genotype or whose kRAS genotype status is unknown in the primary tumour.
- Partial or complete bowel obstruction.
- Chronic diarrhoea or inflammatory bowel disease.
- Gilbert's syndrome or other congenital abnormality of biliary transport (e.g. Crigler-Najjar syndrome, Dubin-Johnson syndrome).
- Previous transplant surgery, requiring immunosuppressive therapy (due to interaction of cyclosporin-A with irinotecan).
- Patients with \geq grade 1 residual neurotoxicity following Oxaliplatin as adjuvant may be offered Irinotecan and 5FU instead of Oxaliplatin and Fluoropyrimidine as neoadjuvant⁴⁵.

9. Treatment of patients

9.a Starting chemotherapy

- Prior to randomisation (i.e. at screening) the chemotherapy regimen to be used (OxMdG or IrMdG) should be selected either according to patient choice or centre policy.
- Following randomisation, patients must start treatment within three weeks (if clinically acceptable) but ideally as soon as possible.
- Appendices I-IV contains protocols for the trial regimens. It is the responsibility of the treating consultant to ensure that these protocols are followed. In particular:
 - Renal, hepatic and bone marrow function must be monitored carefully, and dose-adjustments made as indicated (see AAppendix IV).

- Dose modifications should only be made after consulting appendices I-IV (if in doubt, please discuss with UoSCTU).
- Note that overweight patients are dosed using 1.15 x ideal body weight (see AAppendix II) for all chemotherapy drugs. Cetuximab doses should not however be capped to 1.15 x ideal body weight, please dose according to the patients actual body weight.
- Magnesium levels should be measured in all patients at screening, prior to each chemotherapy cycle and in patients displaying symptoms of hypomagnesemia.

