- FBC and clinical assessment (NCI toxicity scores) should be performed on the day of starting each cycle (or within 3 working days before) and the results available before starting.
- Biochemistry (including creatinine, bilirubin, magnesium and either AST or ALT) is done at the same time as FBC.
- If patient is clinically jaundiced, bilirubin level must be reviewed prior to administration of Oxaliplatin.
- If patient has symptoms of possible hypomagnesemia, check magnesium level and correct as advised (see Appendix XIII).

Toxicity and dose adjustments for OxMdG**Haematological**

- Myelotoxicity occurred in 30% of patients treated with OxMdG in the FOCUS trial.
- Check FBC on (or up to 3 working days before) day 1 of each cycle. Delay 1 week if neutrophils $< 1.5 \times 10^9/l$ or platelets $< 75 \times 10^9/l$. Only treat when neutrophils and platelets are above these limits. The lower limit for the day 1 platelet count for this regimen is due to the possible occurrence of mild thrombocytopenia after a number of cycles of OxMdG.
- If >1 delay, or 1 delay of ≥ 2 weeks occurs, maintain Oxaliplatin and infusional 5FU doses but omit bolus 5FU and continue without bolus 5FU for subsequent doses.
- If a further delay(s) for myelotoxicity occurs despite omitting bolus 5FU reduce the Oxaliplatin and infusional 5FU doses by 20%.
- Further dose reductions may be made, at the discretion of the treating investigator.

Neurotoxicity

- Oxaliplatin commonly causes peripheral sensory symptoms, easily distinguishable from 5FU neurotoxicity, which is uncommon, and cerebellar.
- Many patients experience transient paraesthesia of hands and feet, and some experience dysaesthesia in the throat. These symptoms are precipitated by cold and last from a few hours to a few days after each Oxaliplatin administration. They do not require treatment or dose reduction.
- If symptoms persist until the next cycle is due, and are associated with significant discomfort or loss of function (e.g. dropping objects), omit Oxaliplatin from the regimen and continue with MdG alone. Infusional 5FU should be increased from $2400\text{mg}/\text{m}^2$ to $2800\text{mg}/\text{m}^2$ during this time (any prior 5FU dose reductions should be taken into account). When symptoms have resolved to grade 1, Oxaliplatin should be restarted at the reduced dose of $75\text{mg}/\text{m}^2$ (infusional 5FU should return to normal).

Renal function (see also Appendix IV)

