- If diarrhoea is a problem despite symptomatic treatment, or if more than one delay is required, reduce the Oxaliplatin and 5FU (bolus and infusion) doses by 20% and continue at the lower dose for subsequent cycles unless further toxicity occurs.
- If further toxicity occurs reduce 5FU (bolus and infusion) and Oxaliplatin doses by a further 20%.

Hand-foot syndrome (HFS)

- Treat symptomatically. Pyridoxine 50 mg tds by mouth or topical corticosteroid may help.
- If HFS is still a problem, reduce the 5FU doses (bolus and infusion) by 20% for subsequent cycles.
- If further toxicity occurs reduce 5FU (bolus and infusion) and Oxaliplatin doses by a further 20%.

DPD deficiency; cardiotoxicity

- DPD is the initial and rate-limiting enzyme for 5-FU breakdown. DPD deficiency is an inherited (pharmacogenetic) disorder in which individuals with absent or significantly decreased DPD activity develop life-threatening toxicity following exposure to 5-FU (in either IV or oral form). Reduced drug clearance results in markedly prolonged exposure to 5-FU so that administration of standard doses of 5-FU results in altered 5-FU pharmacokinetics and severe toxicity including mucositis, granulocytopenia, neuropathy and death. The onset of toxicity usually occurs twice as fast in patients with low DPD activity as compared with patients with a normal DPD activity. Approximately 3-5% of the population has low DPD activity and 0.1% have absent activity. We recommend that (i) patients with a personal or family history suggestive of DPD deficiency should not be enrolled onto New EPOC, and (ii) those who experience grade 3/4 neutropenia and grade 3/4 mucositis after cycle 1 should be considered as potentially having DPD deficiency. If DPD deficiency is suspected, patients should only continue on trial after full recovery but without the further use of a Fluoropyrimidine.
- 5FU may provoke angina attacks or even MI in patients with ischaemic heart disease. Continued treatment with upgraded antianginal medication and reduced 5FU dose may be considered.

Allergic reactions to Oxaliplatin

- The occasional patient (approx 0.5%) develops acute hypersensitivity to Oxaliplatin, usually after more than 6 cycles have been administered. During drug administration, the patient may develop rash, fever, swollen mouth or tongue, hypo- or hypertension and other signs/symptoms of hypersensitivity. This rarely develops to full-blown anaphylaxis, even with repeated treatment.

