- Check FBC on (or up to 3 working days before) day 1 of each cycle. Delay 1 week if neutrophils $< 1.5 \times 10^9/l$ or platelets $< 75 \times 10^9/l$. Only treat when neutrophils and platelets are above these limits. The lower limit for the day 1 platelet count for this regimen is due to the possible occurrence of mild thrombocytopenia after a number of cycles of OxMdG.
- If >1 delay, or 1 delay of ≥ 2 weeks occurs, maintain Oxaliplatin and infusional 5FU doses but omit bolus 5FU and continue without bolus 5FU for subsequent doses.
- If a further delay(s) for myelotoxicity occurs despite omitting bolus 5FU reduce Oxaliplatin and infusional 5FU doses by 20%.
- Further dose reductions may be made, at the discretion of the treating investigator.

Neurotoxicity

- Oxaliplatin commonly causes peripheral sensory symptoms, easily distinguishable from 5FU neurotoxicity, which is uncommon, and cerebellar.
- Many patients experience transient paraesthesia of hands and feet, and some experience dysaesthesia in the throat. These symptoms are precipitated by cold and last from a few hours to a few days after each Oxaliplatin administration. They do not require treatment or dose reduction.
- If symptoms persist until the next cycle is due, and are associated with significant discomfort or loss of function (e.g. dropping objects), omit Oxaliplatin from the regimen and continue with MdG plus Cetuximab. Infusional 5FU should be increased from $2400\text{mg}/\text{m}^2$ to $2800\text{mg}/\text{m}^2$ during this time (any prior 5FU dose reductions should be taken into account). When symptoms have resolved to grade 1, Oxaliplatin should be restarted at the reduced dose of $75\text{mg}/\text{m}^2$ (infusional 5FU should return to normal).

Renal function (see also Appendix IV)

- Oxaliplatin, like Carboplatin, is not nephrotoxic but is renally cleared.
- Before starting Oxaliplatin, ensure patient fulfils eligibility for renal function (estimated creatinine clearance [Cockcroft] $>50\text{ml}/\text{min}$ or measured GFR [EDTA clearance] $>50\text{ml}/\text{min}$).
- Check serum creatinine at each cycle. If this rises $>25\%$, re-check EDTA clearance or 24-hour urinary clearance, and adjust Oxaliplatin and 5FU doses according to the table in Appendix IV.
- If GFR drops to below $30\text{ml}/\text{min}$, omit Oxaliplatin and reduce 5FU by 25% until recovery.

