Appendix II – Dose calculations and banding

Overweight patients:

1. Ideal body weight (IBW) is calculated (Lorenz formula) as:
 - i. Men: $IBW \text{ in kg} = [\text{height in cm minus } 100] - [(\text{height} - 150) \div 4]$
 - ii. Women $IBW \text{ in kg} = [\text{height in cm minus } 100] - [(\text{height} - 150) \div 2]$
2. If a patient weighs more than 1.15x their IBW, use 1.15x IBW to calculate surface area (SA).
3. Examples:
 - i. A man is 174 cm tall. His IBW is $174 - 100 - (24 \div 4) = 68 \text{ kg}$. So if his actual weight is less than 78.2 kg (68×1.15), we use his actual weight to calculate SA, but if he weighs more than 78.2 kg, we use 78.2kg to calculate SA (which gives us 1.93 m^2).
 - ii. A woman is 174 cm tall, so her IBW is $74 - 12 = 62 \text{ kg}$. So if she is over 71.3 kg, we use 71.3 kg to calculate SA (this gives us 1.85 m^2)

Fluorouracil dose banding

- First calculate the patient's surface area accurately to 2 decimal places, then calculate the exact target doses for the 5 minute 5FU bolus and 46-hour infusion
 - *For example, a patient of 1.59m^2 receiving the OxMdG regimen without dose-adjustments would have target doses of $400 \times 1.59 = 636 \text{ mg}$ Fluorouracil bolus and $2400 \times 1.59 = 3816 \text{ mg}$ Fluorouracil infusion.*
- Bolus Fluorouracil may then be rounded to the nearest 25 mg, and infusion Fluorouracil may be rounded to the nearest 50 mg.
 - *So the patient in the above example would receive 625 mg bolus + 3800 mg infusion.*
- Fluorouracil may be dose banded up to within 10% where this reflects local practice.

Oxaliplatin dose banding

- As for Fluorouracil, first calculate the patient's surface area accurately to 2 decimal places, then calculate the exact target dose.
 - *For example, the patient of 1.59m^2 receiving the OxMdG regimen without dose-adjustment would have a target dose of $85 \times 1.59 = 135.15 \text{ mg}$*
- The round the Oxaliplatin dose to the nearest 10 mg.
 - *So the patient in the above example would receive 140 mg Oxaliplatin.*

Irinotecan dose banding

- As above, first calculate the patient's surface area accurately to 2 decimal places, then calculate the exact target dose.
 - *For example, the patient of 1.59m² receiving the IrMdG regimen without dose-adjustment would have a target dose of $180 \times 1.59 = 286.2$ mg*
- Irinotecan may be dose banded up to within 5% where this reflects local practice.

Cetuximab dose banding

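### The OxMdG neurotoxicity rule restarts oxaliplatin at a fixed 75 mg/m², a per-cycle rise of about 10% for a patient already cut to 68 mg/m²

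*Protocol*

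**What the plan says.** Appendix I starts oxaliplatin at 85 mg/m² in OxMdG, with or without cetuximab. If sensory symptoms persist until the next cycle is due and are troublesome or limit function, oxaliplatin is omitted and infusional 5FU is raised to 2800 mg/m². For 5FU the bullet adds that "any prior 5FU dose reductions should be taken into account". It then says: "When symptoms have resolved to grade 1, Oxaliplatin should be restarted at the reduced dose of" 75 mg/m². The wording on these points is the same in both arms, and neither bullet has a matching clause for oxaliplatin.

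The same appendix cuts oxaliplatin for other toxicities:

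- **Diarrhoea, both arms:** "reduce the Oxaliplatin and 5FU (bolus and infusion) doses by 20% and continue at the lower dose for subsequent cycles unless further toxicity occurs". The next step is "If further toxicity occurs reduce 5FU (bolus and infusion) and Oxaliplatin doses by a further 20" per cent.
- **Myelotoxicity:** if there is a further delay "despite omitting bolus 5FU reduce the Oxaliplatin and infusional 5FU doses by 20" per cent (OxMdG), or "despite omitting bolus 5FU reduce Oxaliplatin and infusional 5FU doses by 20" per cent (OxMdG plus cetuximab).
- **Stomatitis and hand-foot syndrome, both arms:** the first step cuts only 5FU. Oxaliplatin is cut by 20% at the second step.

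Section 9.b lets the investigator reintroduce oxaliplatin with caution after neuropathy, but gives no dose. Section 9.a says of dose modifications: "if in doubt, please discuss with UoSCTU".

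**The concern.** The restart rule is meant to bring a patient back on less oxaliplatin per cycle after neuropathy. It does so only if the patient was at, or close to, full dose beforehand. The authors foresaw earlier reductions, because the same bullet covers them for 5FU, but they left oxaliplatin uncovered. One standard 20% cut already puts the patient below 75 mg/m². Someone who follows the figure would then give a higher dose of a neurotoxic drug than the one on which the neuropathy became troublesome, in a patient whose regimen had already been cut for toxicity. What is at stake is a patient-safety dosing rule, not the analysis.

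**Working it through.** **Inputs.** Full dose 85 mg/m², restart dose 75 mg/m² and cut size 20% come from Appendix I. The rounding rule, "round the Oxaliplatin dose to the nearest 10 mg", and the example surface areas 1.59, 1.85 and 1.93 m² come from Appendix II. Planned treatment is 12 weeks before and 12 weeks after surgery (section 9.b) in 14-day cycles (Appendix I), so 24/2 = 12 cycles.

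**1. The plan's own description.** 75/85 = 0.882. From full dose, 75 mg/m² is an 11.8% reduction, so the term *reduced dose* is right for that patient. It also follows that any earlier cut larger than 11.8% turns the restart into a rise.

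**2. After one 20% cut.** 85 × 0.80 = 68 mg/m². 75/68 = 1.103, a rise of 10.3% per cycle.

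**3. After rounding to 10 mg.**

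| Surface area | Full dose (85) | Restart (75) | After one cut (68) |
|---|---|---|---|
| 1.59 m² | 135.15 → 140 mg | 119.25 → 120 mg | 108.12 → 110 mg |
| 1.85 m² | 157.25 → 160 mg | 138.75 → 140 mg | 125.80 → 130 mg |
| 1.93 m² | 164.05 → 160 mg | 144.75 → 140 mg | 131.24 → 130 mg |

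Rounding does not remove the rise. It is 10 mg each time, and the restart dose is still 20 mg below the rounded full dose.

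**4. Total oxaliplatin after one cut.** Compare omitting a cycle and restarting at 75 mg/m² with continuing at 68 mg/m². Each restarted cycle adds 75 − 68 = 7 mg/m², and the omitted cycle loses 68 mg/m². Break-even is 68/7 = 9.7 restarted cycles. If at least one cycle was given at 85 mg/m², at least one at 68 mg/m² and at least one omitted, at most 12 − 3 = 9 cycles remain. 9 × 7 = 63 mg/m², which is less than 68 mg/m². So the per-cycle dose rises and the total does not.

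**5. The rules side by side.** After a diarrhoea cut, the diarrhoea bullets keep the patient at 68 mg/m², or cut further if neuropathy counts as further toxicity. Either way the dose is at most 68 mg/m², while the neurotoxicity bullet gives 75 mg/m². The two cannot both be followed. After a myelotoxicity cut, or a second-step stomatitis or hand-foot cut, no sentence tells the clinician to hold oxaliplatin at the lower level. There the 75 mg/m² is a re-escalation that the bullet does not appear to intend, but not a contradiction in the text.

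**The case against.** The strongest reply is that the bullet calls 75 mg/m² a reduced dose, so it presupposes a patient at 85 mg/m². On that reading it is silent about a patient on 68 mg/m² rather than ordering a rise. This shows what was intended, but the sentence still gives one figure without a condition and nothing caps it.

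A second reply is that a careful clinician would read the diarrhoea and neurotoxicity bullets as limits that both apply, and would stay at 68 mg/m². Discretion is also wide. Section 9.b makes reintroduction optional, section 9.a invites a call to the trials unit, section 21.b leaves the investigator free to depart from protocol treatment, and the haematological bullets allow further reductions. All of this stands as a reason why an actual rise is unlikely. None of these places states a dose or an upper limit. Appendix I also suggests copying the relevant schedule into the patient's notes, so the bullet may be read without section 9.b beside it.

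A third reply is that the route is narrow. The patient needs an earlier oxaliplatin cut, then persistent neuropathy, then recovery to grade 1 with cycles left. That is fair, and it limits the weight of the point.

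A reader might go further and infer that the rule increases a patient's overall oxaliplatin exposure. For a single earlier cut the documents do not support that, because the omitted cycle outweighs what the restarted cycles add (step 4). A reader might also infer a bias between arms. The rule is the same in both arms, so nothing in the protocol supports an effect on the progression-free survival comparison.

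**Conclusion.** The point holds as a minor dosing-rule error. In both OxMdG sections the fixed 75 mg/m² restart makes no allowance for an earlier oxaliplatin cut. Followed as written after one 20% cut, it raises the per-cycle dose by 10.3%, or one 10 mg step at the protocol's example surface areas. It contradicts the stay-low instruction after a diarrhoea cut and is an unintended per-dose re-escalation after the other cuts.

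The size rests on a single 20% cut from full dose. The statement about total oxaliplatin also assumes the planned 12 cycles, with at least one given at each dose level before the omission. The protocol does not give the size of the affected group, which is probably small. Practical urgency is limited too: section 14 expected recruitment to finish at the end of December 2012, so few or no patients may still be on treatment.

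**What to change.** In the neurotoxicity bullets for OxMdG and for OxMdG plus cetuximab, write: *restart at 75 mg/m² or the patient's oxaliplatin dose before the interruption, whichever is lower*. A patient who was at 85 mg/m² still restarts at 75 mg/m², and a patient who was at 68 mg/m² restarts at no more than 68 mg/m². The clause only prevents a rise. Whether someone already below 75 mg/m² should step down further (for example to 75 × 0.80 = 60 mg/m², carrying the earlier cut through) is a clinical decision for the trial team. The cost is one clause in each of two bullets, issued as a protocol clarification, with no change to procedures, data collection or analysis.
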